10.3.1 Definition of AE

AE Definition

- An AE is any untoward medical occurrence in a patient or clinical study participant, temporally associated with the use of study medication, whether or not considered related to the study medication.
- NOTE: An AE can therefore be any unfavorable and unintended sign (including an abnormal laboratory finding), symptom, or disease (new or exacerbated) temporally associated with the use of study medication.

Events Meeting the AE Definition

- Any abnormal laboratory test results (hematology, clinical chemistry, or urinalysis) or other safety assessments (eg, ECG, radiological scans, vital signs measurements), including those that worsen from Baseline, considered clinically significant in the medical and scientific judgment of the Investigator (ie, not related to progression of underlying disease).
- Exacerbation of a chronic or intermittent pre-existing condition including either an increase in frequency and/or intensity of the condition.
- New conditions detected or diagnosed after study medication administration even though it may have been present before the start of the study.
- Signs, symptoms, or the clinical sequelae of a suspected drug-drug interaction.
- Signs, symptoms, or the clinical sequelae of a suspected overdose of either study medication or a concomitant medication. Overdose per se will not be reported as an AE/SAE unless it is an intentional overdose taken with possible suicidal/self-harming intent. Such overdoses should be reported regardless of sequelae.

Events NOT Meeting the AE Definition

- Any clinically significant abnormal laboratory findings or other abnormal safety assessments which are associated with the underlying disease, unless judged by the Investigator to be more severe than expected for the study participant's condition.
- The disease/disorder being studied or expected progression, signs, or symptoms of the disease/disorder being studied, unless more severe than expected for the study participant's condition.
- Medical or surgical procedure (eg, endoscopy, appendectomy): the condition that leads to the procedure is the AE.
- Situations in which an untoward medical occurrence did not occur (social and/or convenience admission to a hospital).
- Anticipated day-to-day fluctuations of pre-existing disease(s) or condition(s) present or detected at the start of the study that do not worsen.

10.3.2 Definition of SAE

If an event is not an AE per definition above, then it cannot be an SAE even if serious conditions are met (eg, hospitalization for signs/symptoms of the disease under study, death due to progression of disease).

A SAE is defined as any untoward medical occurrence that, at any dose:

a. Results in death

b. Is life-threatening

The term ‘life-threatening’ in the definition of ‘serious’ refers to an event in which the study participant was at risk of death at the time of the event. It does not refer to an event, which hypothetically might have caused death, if it were more severe.

c. Requires inpatient hospitalization or prolongation of existing hospitalization

In general, hospitalization signifies that the study participant has been detained (usually involving at least an overnight stay) at the hospital or emergency ward for observation and/or treatment that would not have been appropriate in the physician’s office or outpatient setting. Complications that occur during hospitalization are AEs. If a complication prolongs hospitalization or fulfills any other serious criteria, the event is serious. When in doubt as to whether “hospitalization” occurred or was necessary, the AE should be considered serious.

Hospitalization for elective treatment of a pre-existing condition that did not worsen from Baseline is not considered an AE.

d. Results in persistent disability/incapacity

- The term disability means a substantial disruption of a person’s ability to conduct normal life functions.
- This definition is not intended to include experiences of relatively minor medical significance such as uncomplicated headache, nausea, vomiting, diarrhea, influenza, and accidental trauma (eg, sprained ankle) which may interfere with or prevent everyday life functions but do not constitute a substantial disruption.

e. Is a congenital anomaly/birth defect

f. Important medical events:

- Medical or scientific judgment should be exercised in deciding whether SAE reporting is appropriate in other situations such as important medical events that may not be immediately life-threatening or result in death or hospitalization but may jeopardize the study participant or may require medical or surgical intervention to prevent one of the other outcomes listed in the above definition. These events should usually be considered serious.

Examples of such events include, but are not limited to, potential Hy’s law, invasive or malignant cancers, intensive treatment in an emergency room or at home for allergic bronchospasm, blood dyscrasias or convulsions that do not result in hospitalization, or development of drug dependency or drug abuse.

10.3.3 Recording and follow-up of AE and/or SAE

AE and SAE Recording

- When an AE/SAE occurs, it is the responsibility of the Investigator to review all documentation (eg, hospital progress notes, laboratory reports, and diagnostics reports) related to the event.
- The Investigator will then record all relevant AE/SAE information in the eCRF.
- It is **not** acceptable for the Investigator to send photocopies of the study participant's medical records to UCB in lieu of completion of the UCB/AE/SAE eCRF page.
- There may be instances when copies of medical records for certain cases are requested by UCB. In this case, all study participant identifiers, with the exception of the study participant number, will be redacted on the copies of the medical records before submission to UCB.
- The Investigator will attempt to establish a diagnosis of the event based on signs, symptoms, and/or other clinical information. Whenever possible, the diagnosis (not the individual signs/symptoms) will be documented as the AE/SAE.

Assessment of Intensity

The Investigator will make an assessment of intensity for each AE and SAE reported during the study and assign it to 1 of the following categories:

- **Mild:** An event that is easily tolerated by the study participant, causing minimal discomfort and not interfering with everyday activities.
- **Moderate:** An event that causes sufficient discomfort and interferes with normal everyday activities.
- **Severe:** An event that prevents normal everyday activities. An AE that is assessed as severe should not be confused with a SAE. Severe is a category utilized for rating the intensity of an event; and both AEs and SAEs can be assessed as severe.
- An event is defined as 'serious' when it meets at least 1 of the predefined outcomes as described in the definition of an SAE, NOT when it is rated as severe (eg, a severe AE may be either serious or not serious, depending on whether these criteria are also met).

The National Cancer Institute Common Terminology Criteria for Adverse Events should be used as a supportive standardization instrument to evaluate AEs and SAEs but the final intensity grading by the Investigator must be mild, moderate, or severe.

Assessment of Causality

- The Investigator is obligated to assess the relationship between study medication and each occurrence of each AE/SAE.
- A “reasonable possibility” of a relationship conveys that there are facts, evidence, and/or arguments to suggest a causal relationship, rather than a relationship cannot be ruled out.
- The Investigator will use clinical judgment to determine the relationship.
- Alternative causes, such as underlying disease(s), concomitant therapy, and other risk factors, as well as the temporal relationship of the event to study medication administration will be considered and investigated.
- The Investigator will also consult the IB and/or Product Information, for marketed products, in his/her assessment.
- For each AE/SAE, the Investigator **must** document in the medical notes that he/she has reviewed the AE/SAE and has provided an assessment of causality.
- There may be situations in which an SAE has occurred and the investigator has minimal information to include in the initial report to UCB. However, **it is very important that the Investigator always make an assessment of causality for every event before the initial transmission of the SAE data to UCB.**
- The Investigator may change his/her opinion of causality in light of follow-up information and send a SAE follow-up report with the updated causality assessment.
- The causality assessment is one of the criteria used when determining regulatory reporting requirements.

Follow-up of AEs and SAEs

- The Investigator is obligated to perform or arrange for the conduct of supplemental measurements and/or evaluations as medically indicated or as requested by UCB to elucidate the nature and/or causality of the AE or SAE as fully as possible. This may include additional laboratory tests or investigations, histopathological examinations, or consultation with other health care professionals.
- An AE should be followed until it has resolved, has a stable sequelae, the Investigator determines that it is no longer clinically significant, or the study participant is lost to follow up. This follow-up requirement applies to AEs, SAEs, and AEs of special interest.
- If a study participant dies during participation in the study or during a recognized follow-up period, the Investigator will provide UCB with a copy of any post-mortem findings including histopathology.
- New or updated information will be recorded in the originally completed eCRF.
- The Investigator will submit any updated SAE data to UCB within 24 hours of receipt of the information.

Reporting of SAEs

SAE Reporting to UCB via an Electronic Data Collection Tool

- The primary mechanism for reporting an SAE to UCB will be the electronic data collection tool.
- If the electronic system is unavailable for more than 24 hours, then the site will use the paper SAE data collection tool (see next section).
- The site will enter the SAE data into the electronic system as soon as it becomes available.
- After the study is completed at a given site, the electronic data collection tool will be taken off-line to prevent the entry of new data or changes to existing data.
- If a site receives a report of a new SAE from a study participant or receives updated data on a previously reported SAE after the electronic data collection tool has been taken off-line, then the site can report this information on a paper SAE form (see next section) or to the UCB Study Physician by telephone.
- Contacts for SAE reporting can be found in [SERIOUS ADVERSE EVENT REPORTING](#).

SAE Reporting to UCB via Paper CRF

- Facsimile transmission of the SAE paper CRF is the preferred method to transmit this information to the UCB Study Physician.
- In rare circumstances and in the absence of facsimile equipment, notification by telephone is acceptable with a copy of the SAE data collection tool sent by overnight mail or courier service.
- Initial notification via telephone does not replace the need for the Investigator to complete and sign the SAE CRF pages within the designated reporting time frames.
- Contacts for SAE reporting can be found in [SERIOUS ADVERSE EVENT REPORTING](#).

10.4 Appendix 4: Contraceptive guidance and collection of pregnancy information

10.4.1 Definitions

10.4.1.1 Woman of childbearing potential

A woman is considered fertile following menarche and until becoming post-menopausal unless permanently sterile (see below).

Women in the following categories **are not considered WOCBP**:

1. Premenarchal
2. Premenopausal female with 1 of the following:
 - Documented hysterectomy
 - Documented bilateral salpingectomy
 - Documented bilateral oophorectomy

Note: Documentation can come from the site personnel's review of the study participant's medical records, medical examination, or medical history interview.

3. Postmenopausal female
 - A postmenopausal state is defined as no menses for 12 months without an alternative medical cause. A high follicle stimulating hormone (FSH) level in the postmenopausal range may be used to confirm a postmenopausal state in women not using hormonal contraception or HRT. However, in the absence of 12 months of amenorrhea, a single FSH measurement is insufficient.
 - Females on HRT and whose menopausal status is in doubt will be required to use one of the non-estrogen hormonal highly effective contraception methods if they wish to continue their HRT during the study. Otherwise, they must discontinue HRT to allow confirmation of postmenopausal status before study enrollment.

10.4.2 Contraception guidance

10.4.2.1 Male participants

Male study participants with female partners of childbearing potential are eligible to participate if they agree to ONE of the following during the protocol-defined time frame in Section 5.1:

- Are abstinent from penile-vaginal intercourse as their usual and preferred lifestyle (abstinent on a long term and persistent basis) and agree to remain abstinent.
- Agree to use a male condom plus partner use of a contraceptive method with a failure rate of <1% per year as described in Table 10-1 when having penile-vaginal intercourse with a WOCBP who is not currently pregnant.

In addition, male study participants must refrain from donating sperm for the duration of the study and for 7 days after the final dose of study medication.

Male participants with a pregnant or breastfeeding partner must agree to remain abstinent from penile-vaginal intercourse or use a male condom during each episode of penile penetration during the protocol-defined time frame and for 90 days after the final dose of study medication.

10.4.2.2 Pregnancy testing

- Women of childbearing potential should only be included after a confirmed menstrual period and a negative highly sensitive serum pregnancy test.
- Pregnancy testing will be performed whenever a menstrual cycle is missed or when pregnancy is otherwise suspected.
- Serum beta human chorionic gonadotropin (HCG) pregnancy testing will be performed at Screening.
- Additional urine beta HCG pregnancy testing will be performed at Baseline and on Day 11 of the MD Treatment Period. The result must be negative prior to dosing the study participant.

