1.3 Schedule of activities

The schedule of activities is provided in [Table 1-2](#).

Table 1-2: Schedule of activities

Study Period/Visit	Scr	BL Visit	Treatment Period														Follow-up Period		
			Period 1A (SD)					Period 1B (MD)									EOS/EOT Visit		
Study Day(s)	-28 to -3	-1	1	2	3	4	5-7	8	9	10	11	12	13	14	15	16	17-21	22	
			Washout															Washout	
Procedures																			
Written Informed Consent	X																		
Demographics & baseline characteristics	X	X																	
Inclusion/exclusion criteria verification	X	X																	
General medical/procedures history	X	X																	
Study Participant Identification Card assigned		X																	
Suicidality risk evaluation (C-SRSS) ^a	X	X				X										X			X
Physical examination ^b	X	X	X			X		X								X			X
Psychiatric and Mental Status	X	X	X	X	X	X		X	X	X	X	X	X	X	X	X			X
Vital signs ^c	X	X	X				X	X	X	X	X	X	X	X	X	X			X
Pregnancy test ^d	X	X																	X
Hematology, serum chemistry, urinalysis ^e	X	X				X		X					X			X			X
Serology (HIV, Hep B & C)	X																		
12-lead ECG ^f	X	X	X					X	X	X	X	X	X	X	X	X			
Urine and cotinine drug screen, alcohol breath test	X	X						X											
Recording of AEs /medical procedures	X	X	X	X	X	X	X	X	X	X	X	X	X	X	X	X	X	X	X

Table 1-2: Schedule of activities

Study Period/Visit	Scr	BL Visit	Treatment Period															Follow-up Period	
			Period 1A (SD)					Period 1B (MD)										EOS/EOT Visit	
Study Day(s)	-28 to -3	-1	1	2	3	4	5-7	8	9	10	11	12	13	14	15	16	17-21	22	
			Washout															Washout	
Procedures																			
Admit to study center		X ^g					X ^g												
Discharge from study center							X ^g										X ^g	X	
Administer PSL			X					X	X	X	X	X	X	X	X	X			
Study drug accountability			X						X	X	X	X	X	X	X	X			
Blood sampling for PSL PK levels ^h			X	X	X	X							X						
Additional blood sampling for PPB ⁱ													X						
Urine collection for PSL PK ^j			X	X	X	X							X						
Final disposition determination ^k																			X

AE=adverse event; BID=twice daily; BL=Baseline; C-SSRS=Columbia-Suicide Severity Rating Scale; ECG=electrocardiogram; EOS=End-of-Study;

EOT=End-of-Treatment; Hep=hepatitis; HIV=human immunodeficiency virus; MD=multiple dose; PK=pharmacokinetic(s); PPB=plasma protein binding; PSL=padsevonil; Scr=screening; SD=single dose; t_{max}=time to maximum plasma concentration

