^a All study participants will complete the “Screening/Baseline” version of the C-SSRS during Screening (assessing the past 6 months) and Baseline (Day -1), followed by the “Since Last Visit” version at subsequent visits.

^b At Screening, Baseline (Day -1) and Day 8, a full physical examination will be performed. On all other days a physical examination is performed, it will be a short physical examination (see Section 8.3.4).

^c Vital signs will be performed before each morning dose of PSL; if feasible; vital sign evaluations will follow the same schedule as ECGs. Blood pressure and pulse measurements should be preceded by at least 5 minutes of rest for the study participant in a quiet setting without distractions (eg, television, cell phones).

^d Serum pregnancy test will be performed for females of childbearing potential at Screening. Urine pregnancy testing will be performed at all other time points indicated.

^e For safety laboratory evaluations that occur on a dosing day, these will be performed before the morning dose/PK sample collection.

^f A 12-lead ECG will be performed after a rest of at least 5 minutes. All ECG recordings will be performed in triplicate at 2 to 3 minute intervals at Screening, Baseline (Day -1), predose and 3 hours after the morning dose on each PSL dosing day and EOS/EOT Visit.

- ^g Study participants will be confined to the study site starting at Baseline (Day -1) and may be discharged on the morning of Day 5 after the assessments are complete, per the discretion of the Investigator. Study participants discharged on Day 5 will be readmitted to the study site on the evening of Day 7. If the Investigator deems it acceptable, study participants may be discharged the morning of Day 17.
- ^h PK plasma samples will be taken at the following time points: (a) Period 1A (single dose): predose on Day 1 and 0.25, 0.5, 0.75, 1, 1.5, 3, 4, 6, 8, 12, 24, 48, and 72 hours postdose (14 samples); (b) Period 1B (multiple doses): predose (morning dose), and 0.25, 0.5, 0.75, 1, 1.5, 3, 4, 6, 8, and 12h after the morning dose (11 samples).
- ⁱ Two blood samples will be collected after multiple doses at steady state (Day 13 predose and 1.5h postdose[$\sim t_{max}$]) for PPB.

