7.2 Participant discontinuation/withdrawal from the study

Study participants are free to withdraw from the study at any time, without prejudice to their continued care.

A study participant may withdraw from the study at any time at his/her own request, or may be withdrawn at any time at the discretion of the Investigator for safety, behavioral, compliance, or administrative reasons.

If the study participant withdraws consent for disclosure of future information, the Sponsor may retain and continue to use any data collected before such a withdrawal of consent.

If a study participant withdraws from the study, he/she may request destruction of any samples taken and not tested, and the Investigator must document this in the site study records.

See the Schedule of Activities (Table 1-2) for data to be collected at the time of study discontinuation and follow-up and for any further evaluations that need to be completed.

Study participants should be withdrawn from the study if any of the following events occur:

1. The study participant develops a clinically relevant medical condition (physical or psychiatric) that, in the opinion of the Investigator, jeopardizes or compromises the study participant's ability to participate in the study or makes it unsafe to continue.
2. The study participant is noncompliant with the study procedures or medications in the opinion of the Investigator.
3. The study participant takes prohibited concomitant medications as defined in this protocol.
4. The study participant withdraws his or her consent.
5. There is confirmation of a pregnancy during the study, as evidenced by a positive pregnancy test.
6. The Sponsor or a regulatory agency requests withdrawal of the study participant.
7. The study participant has changes in the ECG that are regarded as clinically significant and/or that worsens over time.
8. The study participant has an ECG that shows an absolute value for QTcB or QTcF ≥ 500 ms or ≥ 60 ms above Baseline.
9. The study participant develops a second- or third-degree atrioventricular block or another clinically relevant change in ECG as determined by the Investigator.

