8 STUDY ASSESSMENTS AND PROCEDURES

Study procedures and their timing are summarized in the Schedule of Activities ([Table 1-2](#)).

Protocol waivers or exemptions are not allowed.

Immediate safety concerns should be discussed with the Sponsor immediately upon occurrence or awareness to determine if the study participant should continue or discontinue study treatment.

Adherence to the study design requirements, including those specified in the Schedule of Activities ([Table 1-2](#)), is essential and required for study conduct.

All Screening evaluations must be completed and reviewed to confirm that potential study participants meet all eligibility criteria. The Investigator will maintain a screening log to record details of all study participants screened and to confirm eligibility or record reasons for screening failure, as applicable.

Procedures conducted as part of the study participant's routine clinical management (eg, blood count) and obtained before signing of the ICF may be utilized for screening or baseline purposes provided the procedures met the protocol-specified criteria and were performed within the time frame defined in the Schedule of Activities ([Table 1-2](#)).

The maximum amount of blood collected from each study participant over the duration of the study, including any extra assessments that may be required, will not exceed 500mL. Repeat or unscheduled samples may be taken for safety reasons or for technical issues with the samples.

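### Protocol 10.4.2.2 requires a Day 11 urine pregnancy test, negative before dosing, that Table 1-2 does not schedule, and it leaves out the Day 22 test that the table does schedule

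*Protocol*

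**What the plan says.** Protocol 10.4.2.2 sets a serum test at Screening and then: "Additional urine beta HCG pregnancy testing will be performed at Baseline and on Day 11 of the MD Treatment Period". The next sentence attaches a condition: "The result must be negative prior to dosing the study participant". The same list has an event-driven rule: "Pregnancy testing will be performed whenever a menstrual cycle is missed or when pregnancy is otherwise suspected".

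In Table 1-2 (Protocol 1.3) the pregnancy test row is marked at Screening, at Baseline (Day -1) and in the final EOS/EOT column (Day 22). Nothing is marked from Day 1 to Day 21. Footnote d assigns the serum test to Screening and continues: "Urine pregnancy testing will be performed at all other time points indicated". SAP Table 2-1 has the same marks and the same footnote.

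On follow-up of a pregnancy, Protocol 8.4.5 collects details up to 30 days after birth, lets the Sponsor ask for longer in some circumstances, and sends the Investigator to Appendix 4. Sections 10.4.2.3.2 (partners) and 10.4.2.3.3 (participants) of that appendix set a general period of at least 12 months from delivery.

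**The concern.** The appendix and the schedule list different test days, and the difference runs both ways: Day 11 appears only in the appendix, Day 22 only in the schedule. The Day 11 test matters more because the appendix makes its result a condition for dosing. A site that builds its visit worksheets from Table 1-2 would not plan it, and would deviate from Appendix 4 by following the schedule.

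At stake is the check during dosing. Withdrawal criterion 5 in Protocol 7.2 reads: "There is confirmation of a pregnancy during the study, as evidenced by a positive pregnancy test". With no test scheduled between Day -1 and the last dose on Day 16, only an unscheduled test could trigger that criterion while PSL is being given. These are healthy volunteers with no medical benefit from taking part (Protocol 2.3), so the instruction should be unambiguous.

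**Working it through.** The plan states no figure to reproduce. The check compares the two lists of test days and then counts days.

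**1. The lists side by side**

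| Time point | Protocol 10.4.2.2 | Table 1-2 and SAP Table 2-1 |
|---|---|---|
| Screening | serum | marked |
| Baseline (Day -1) | urine | marked |
| Day 11 | urine, negative before dosing | not marked |
| Day 22 (EOS/EOT) | not listed | marked |

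**2. Which day is Day 11?** Period 1B starts on Day 8 (Protocol 4.1.2). There are two readings:
- Study Day 11: dosing at 200mg BID.
- The 11th day of Period 1B: 8 + 11 - 1 = study Day 18. This is in the Day 17 to 21 washout, after the last dose on Day 16, and after participants may have been discharged on the morning of Day 17.

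A test whose result must be negative before a dose makes sense only on study Day 11. Neither day is marked in either table, so the mismatch exists on both readings.

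**3. Scheduled tests after the first dose and up to the last dose (Day 1 to Day 16)**
- Table 1-2: 0.
- 10.4.2.2, study Day 11 reading: 1.
- 10.4.2.2, study Day 18 reading: 0.

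**4. Gap between scheduled tests.** There is no Day 0, so Day -1 is one day before Day 1.
- Table 1-2: Day -1 to Day 22 is 1 + (22 - 1) = 22 days.
- With study Day 11 added: 1 + (11 - 1) = 11 days, then 22 - 11 = 11 days.

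**5. What the Day 11 test could find.** Footnote g allows discharge from the morning of Day 5, and: "Study participants discharged on Day 5 will be readmitted to the study site on the evening of Day 7". A conception in that window would be 11 - 7 = 4 to 11 - 5 = 6 days old on study Day 11, so the test could not be relied on to show it. The other target is a conception too recent to show on Day -1.

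**6. Number of tests added.** Cohort A plans 10 adults with at least 3 of each sex, so 3 to 10 - 3 = 7 women. An even split, which the protocol aims for, gives about 5. Only those of childbearing potential are tested. This assumes that women aged 65 or over in Cohort B are postmenopausal.

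**7. Follow-up after a pregnancy.** 30 days against about 365 days, a difference of 365 - 30 = 335 days in the stated default.

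**The case against.** The strongest reply is that the protocol already directs a careful site to the right place. Inclusion criterion 5 refers to Appendix 4 for women of childbearing potential, Appendix 2 allows additional laboratory tests at any time, and testing on a missed period or suspicion is required. This stands, and it limits the consequences. It does not remove the difference between the two lists.

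A reader might infer that Section 8 makes the schedule override the appendix, since adherence "is essential and required for study conduct". It does not. That sentence covers the study design requirements in general and names the schedule as one part of them, so it does not rank Table 1-2 above Appendix 4. Nor does footnote d forbid a test on an unmarked day; it only says which test is used at the marked ones.

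It can also be said that dropping Day 11 from 10.4.2.2 and listing Day 22 would restore consistency equally well, and that nothing shows which text was intended. That is fair. Keeping Day 11 is preferred because it is the only test fixed in advance that could fall during dosing, and it costs almost nothing.

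On follow-up, 8.4.5 itself points to Appendix 4, so a site that follows the reference would satisfy both. What remains is two different stated defaults, which matter only if a pregnancy occurs.

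Finally, the SAP cites clarification memos of 11 June and 11 September 2019 that are not among the documents. They may address this. That SAP Table 2-1 is unchanged in a SAP approved on 20 September 2019 does not show what they say.

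**Conclusion.** The inconsistency is real and worth correcting. Appendix 4 makes a test on Day 11 a condition for dosing, the schedule omits it, and the appendix omits the scheduled Day 22 test. The count of one required test against none scheduled during dosing, and the 11-day intervals, rest on reading the day as study Day 11. The condition about dosing supports that reading, but the wording does not state it. On the Day 18 reading the mismatch remains, but neither text places a test during dosing after Day 1.

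The documents do not support the stronger inference that women would be left without pregnancy safeguards. Confinement, contraception rules, the Baseline test and testing on suspicion all apply, so the practical gain from the Day 11 test is small. Nor is there any effect on the PK endpoints, sample size or analyses. The follow-up mismatch is secondary and minor.

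**What to change.** 1. In Table 1-2, add an X for the pregnancy test on study Day 11 and keep Day 22. SAP Table 2-1 only repeats the schedule and can follow at its next revision; sites do not work from it.
2. Reword 10.4.2.2 along these lines: *Urine tests are done at Baseline, on study Day 11 before the morning dose, and at the EOS/EOT Visit (Day 22); the Baseline and Day 11 results must each be negative before the next dose is given.* This also settles which Day 11 is meant.
3. Minor: in 8.4.5, replace the 30-day end point with the Appendix 4 period (generally at least 12 months after delivery) and delete the sentence on extension at the Sponsor's request.

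The cost is one table mark and two short text edits. No procedure is added beyond what Appendix 4 already asks for: at most 7 urine tests with 10 adults in Cohort A, and longer follow-up only if a pregnancy occurs. If the clarification memos already cover the point, the same wording should be carried into the protocol.
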